- b. Sham Threshold Determination (Consent or Randomization Visit): Mouth open, nose breathe only, stimulation from 0.1V up by 0.1-0.2V at same electrode configuration as at last clinic visit, level at which bulk tongue motion detected without obvious protrusion. This process is repeated and the average value is used to determine "sham-HGNS". This threshold will be used to define "sub-therapeutic amplitude" (sham). The electrode configuration will remain consistent between the patient's therapeutic and sham thresholds.
- c. Randomization: The research coordinator will program the device at the specified amplitude level: either "sham-HGNS" as above, or "therapeutic HGNS," depending on which is assigned first (**see part d below**). The "therapeutic HGNS" setting will be the patient's incoming amplitude on enrollment day which will have been predetermined as part of routine clinical care prior to enrollment in the study. The patient control range will be deactivated for consistency, i.e. there will only be one allowable setting. The research coordinator will instruct the patient to use therapy the same night, and for every night until the next washout after cardiovascular test day (study week 6).
- d. Randomization technique: Both patients and investigators will remain blinded regarding patient intervention (sham or treatment HGNS). Only the research coordinator will remain unblinded; he will randomize the patients using a simple scheme (sealedenvelope.com) and will not take part in any assessments. Block design (block size = 10 with 10 units per block) for total of 100 potential subjects. Number 1 = Sham First, Number 2 = Treatment First.
- Blinding Adequacy Phone Call (Week 2, Day 2)

A blinded member of the study team, as delegated by the PI, will contact the patient and perform a verbal questionnaire:

- 1. Do you think you are on "low" or "regular" treatment, or do you not know?
- 2. Why you do think so?
 - a. Increased snoring per bed partner
 - b. Increased fatigue
 - c. Morning headache
 - d. Nighttime awakening
 - e. Other
- Weekly Check-In Phone Call (Week 3, Week 4, Week 5)

RSC weekly call with patient re: usage. Goal is to encourage use (>20h/week) RSC will document changes in blood pressure medication, if applicable. RSC will remind the patient to consistently take the blood pressure medication. Any questions, comments, concerns, or AEs will be documented at this time as well.

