 Overnight testing: 24-hour Ambulatory Blood Pressure Testing (Study Week 6, Day 0-1), and WatchPAT (Study Week 6, Night 1)

- 1. The patient will be mailed a pre-programmed 24-hour ambulatory blood pressure monitor (ABP) and WatchPAT home sleep test, scheduled to arrive between 2-7 days before physiology testing. For convenience and/or patient preference, the patient may also meet in person with RSC to pick up this equipment. RSC will ensure that ABP, WatchPAT and Inspire® device times are synchronized. Each test will have comprehensive instructions along with a questionnaire (start time, approximate sleep time, wake time, stop time, note anything that may affect the tests). A "blood pressure medication witness" statement will be included in the instructions to ensure that the patient takes the medication on the day of ABP.
- 2. ABP will be measured using a noninvasive, portable, validated recorder (Spacelab 90227; SpaceLabs Medical; Redmond, WA). The patient will wear the device for 24 hours and asked to perform daily activities as usual. The monitor is programmed to record blood pressure every 30 minutes during the day, and every 1 hour at night. Data are considered valid if at least 50% of the readings over the 24 hours are adequate, with at least 16 hours of use, or at the discretion of the PI. The patient will be asked to record bedtime and wake time to corroborate the sleep and wake time from the recorder. The following night, the patient will perform the WatchPAT test. The patient will be advised not to use both at same time. The patient must use HGNS at same time as WatchPAT. RSC will follow up with patient to ensure both were completed to best of subject's ability.
- 3. The following day, the patient will return to the lab to return the ABP and WatchPAT equipment and undergo vascular, sympathetic, and neurobehavioral measurements. If any of the ABP or WatchPAT data is invalid or incomplete, the patient may be asked to repeat these tests, at the discretion of the PI. Therefore, the patient will remain at the current setting and will return to have their HGNS reset for therapy washout.

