 - 5. Exit Questionnaire
 - 6. The patient will resume usual care: the RSC will reprogram the patient's HGNS to the pre-study therapeutic amplitude and will reactivate the stimulation control range. The patient will be encouraged to contact the study team to address any problems or questions.

5. Variables:

Medical Chart: age, sex, race, smoking status, hypertension status, diabetes status, apnea-hypopnea index (AHI) from pre-operative sleep study, ODI from pre-operative study, pre-operative DISE report, history of PAP intolerance

Study Data (Clinical): body-mass index, current medications (recorded each study visit), therapy usage (hours/week)

Study Data (Experimental): mean systolic and diastolic blood pressures over 24 hours, mean systolic and diastolic blood pressures during sleep, WatchPAT ODI and AHI from both sham and active therapy tests, pre-ejection period (milliseconds), flow-mediated dilation, peripheral arterial stiffness (PWV in m/s, AIX, SEVR), Snoring Visual Analog Scale (VAS), Epworth Sleepiness Scale (ESS), Insomnia Severity Index (ISI), Functional Outcomes Sleep Questionnaire (FOSQ-10)

6. Analysis

The overall analysis plan is to examine changes in all cardiovascular endpoints over time (i.e., sham to treatment or treatment to sham) as well as internal correlation of these endpoints. Sex, a relevant biological variable, is a covariate in all analyses.

For **Aim 1**, we will perform a paired t-test to compare sham and active therapy 24-hour systolic ambulatory blood pressure values. Improvement in AHI will be calculated as the

difference between pre-operative and post-operative AHI. Multivariable linear regression models will be used to estimate associations between blood pressure reduction (outcome variable) and improvement in AHI (main effect variable) Final models will include age, sex, body-mass index, baseline systolic BP, baseline diastolic BP, antihypertensive medication use.

- H1: Therapeutic levels of HGNS will reduce mean 24-hour systolic pressures
- **H2:** Therapeutic levels of HGNS will further reduce mean sleep systolic and diastolic pressures

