For Hypotheses 1 & 2, for the purposes of sample size estimation, we are using t-test (bivariate) calculation rather than multivariate analysis. Historical data from an OSA cohort demonstrated an overall 24-hour mean systolic pressure of 133mmHg, with a standard deviation=11. 40 We estimate a clinically significant difference in systolic blood pressure to be 4mmHg⁴¹ which, at the population level, reduces mortality from stroke by 10-40% and mortality from ischemic heart disease or other vascular causes by 7-10%. 42 With significance level α = 0.05 (two-tailed) and power 1- β = 0.80, to test a difference in blood pressure of 4mmHg between two repeated measures, a sample of **n=60** would be needed.

For **Aim 3**, we will perform paired t-tests to compare sham and therapy values for both MSNA bursts/minute and pre-ejection period duration. Note that MSNA will no longer be performed at the University of Pennsylvania.

H1: Therapeutic levels of HGNS will reduce muscle sympathetic nerve activity, a direct measure of sympathetic activity

**H2**: Therapeutic levels of HGNS will increase the duration of the pre-ejection period, an indirect measure of sympathetic activity

For the purposes of sample size estimation for H1, in a published study of OSA patients measuring baseline MSNA, mean MSNA was 39 bursts/min (s.d. = 4). ³³ While MSNA is not a commonly used clinical outcome measure, we estimate a significant difference in MSNA to be 5 bursts/min, based on documented effect of CPAP therapy on MSNA. ¹⁴ With significance level α = 0.05 (two-tailed) and power 1- β = 0.80, to test a difference in MSNA of 5 bursts/min between two repeated measures, a sample of **n=11** would be needed.

For Hypothesis 2, published PEP values in a cohort of OSA patients had a mean of 93 milliseconds (s.d.=17.3). ³⁶ Based on comparative data between untreated apneics and non-apneics, we estimate a significant difference in PEP to be a 10 millisecond increase from baseline. ³⁶ With significance level α = 0.05 (two-tailed), power 1- β = 0.80, to test a difference in PEP of 10 milliseconds, a sample of **n=47** would be needed.

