Risk/Benefit Ratio: As there are few risks in measuring cardiovascular data apart from recurrence of OSA symptoms during the 4-week sham period and there are the possible benefits of better understanding sleep apnea and how to treat people with sleep apnea in the future, the risks of participating in this study are outweighed by the potential benefits.

8. Device Management

Penn owns WatchPAT and ambulatory blood pressure devices, which will be managed, dispensed, and received back from subjects by the study team. Recordings will be handled and scored in accordance with best clinical practices.

9. Feasibility

Sample Size Feasibility: We have recruited 17 subjects (16 have successfully completed the study) since January, 2018, and plan to complete recruitment in 2020.

Technical Feasibility: With regard to Aim 1, 16 subjects successfully completed both sets of 24-hour ambulatory blood pressure testing.

Project execution feasibility: PI has 50% protected research time through 2021. PI will devote 20% of his efforts to ensure the successful completion of this project.

10. Potential Pitfalls, Solutions, and Contingency Plans

1. Study Design

a) The study sample reflects a selective subset of patients with moderate-severe OSA, limiting the generalizability of these findings. Among others, the inclusion criteria are 1) unable to consistently use PAP, and 2) body-mass index < 32 kg/m². In clinical practice, this represents only 20% of the moderate-severe OSA population as BMI > 32 kg/m² is an exclusion criterion for HGNS and roughly 50% of patients can comply with PAP. From a population health perspective, however, this selected group represents a not insignificant 2% of the U.S. adult population. ⁴ Note: since this research protocol was created, BMI was

removed as an exclusion criteria for HGNS.

- b) We are performing measurements at 2 time points only, immediately after sham and treatment interventions. While we do not capture baseline values, these measures will allow us to compare the individual effects of sham and active therapy. We predict that a 2-week washout period, in contrast to the 1-week withdrawal period in the STAR trial, ²³ will provide a return to baseline for ABP at 2 weeks. ³¹

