- c) It is plausible that our hypothesis regarding the positive effect of HGNS on blood pressure is not true for two main reasons. First, we are not restricting inclusion for patients with normal blood pressure. Normotensive patients have been shown to have less improvement in blood pressure, compared to hypertensive patients, after CPAP use. ³⁰ Secondly, our prospective cohort data suggests roughly 50% of subjects will be on antihypertensive therapy, potentially masking the blood pressure benefit of HGNS. While we plan to perform multivariate regression controlling for these variables, the sample size will not be sufficient to detect differences in cardiovascular outcomes by subgroup. However, the expected blood pressure values and prevalence of anti-hypertensive medication usage are similar to another OSA cohort in which modest, but significant, improvements were seen with PAP therapy. ⁴³ In exploratory analyses, we can examine patients with baseline hypertension in subgroup analyses.
- d) While we have attempted to blind subjects to each study arm, it is possible that experienced HGNS users will recognize the difference between therapeutic and subtherapeutic HGNS. However, correct guessing of treatment versus sham will not impact the study or the outcomes. Additionally, HGNS users may experience return of untreated OSA symptoms and dropout from the study in order to have therapy restored. Patients will have been thoroughly educated on this aspect of the study prior to enrollment and, as such, we have accounted for 10-15% dropout rate during this period.
- e) We plan to include patients with atrial fibrillation while recognizing the potential challenges in measuring pre-ejection period (Aim 2). By using a 10-minute capture period (~600 data points), we anticipate that this will minimize sample variability.

2. Study Results

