- a) As not all patients will achieve therapeutic success as measured by polysomnography, it is possible that the cardiovascular changes will not be seen in these patients. As part of Aim 1, we will perform linear regression of change in blood pressure upon change in AHI to examine this relationship. As polysomnographic metrics in OSA bear weak a correlation to measures of clinical improvement, ⁴⁴ it is possible that the relationship between AHI and BP reduction is also discordant. If, in fact, there is a discrepancy between cardiovascular outcomes and polysomnographic outcomes, the findings of this study would challenge the current paradigm in outcome measures for OSA.
- b) It is possible that difference between treatment groups is not detected due to the limited sample size (Type II error). This statement applies to Aim 1. If we chose a blood pressure

change of 3mm Hg, instead of 4mm Hg, as a clinically significant difference, our current projected sample size of 60 will be underpowered, $1-\beta = 0.56$. It is noteworthy that the inputs for the sample size and power calculations rely heavily on clinical judgment as poor consensus exists regarding clinically significant differences.

11. Safety and Adverse Events

1. Definitions

- a) Adverse Event/Adverse Device Effect: An adverse event (AE)/adverse device effect (ADE) is any symptom, sign, illness or experience that develops or worsens in severity during the course of the study. Intercurrent illnesses or injuries should be regarded as adverse events. Abnormal results of diagnostic procedures are considered to be adverse events if the abnormality:
 - · results in study withdrawal
 - · Is associated with a serious adverse event
 - · is associated with clinical signs or symptoms
 - · leads to additional treatment or to further diagnostic tests
 - · is considered by the investigator to be of clinical significance
- b) Serious Adverse Event: Adverse events are classified as serious or non-serious. A serious AE is any AE that is:
 - fatal
 - · life-threatening
 - · requires or prolongs hospital stay
 - · results in persistent or significant disability or incapacity
 - required intervention to prevent permanent impairment or damage
 - · a congenital anomaly or birth defect
 - · an important medical event

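### The plan says 10-15% dropout is accounted for, but the primary n=60 matches a paired calculation with no dropout allowance at the only SD given

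*Combined protocol and SAP*

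**What the plan says.** Four places bear on this.

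- **Section 6, sample size for Hypotheses 1 and 2.** The inputs are two-sided alpha 0.05, power 0.80 and a difference of 4 mmHg. The SD comes from this sentence: "Historical data from an OSA cohort demonstrated an overall 24-hour mean systolic pressure of 133mmHg, with a standard deviation=11". The calculation is framed as one "to test a difference in blood pressure of 4mmHg between two repeated measures", and 60 is given as its result. No dropout step is shown.
- **Section 6, Aim 1.** The analysis is paired: "we will perform a paired t-test to compare sham and active therapy 24-hour systolic ambulatory blood pressure values".
- **Section 10, item 1(d).** Patients may leave to have therapy restored, and the plan says that "we have accounted for 10-15% dropout rate during this period".
- **Section 10, item 2(b).** For a 3 mmHg difference, "our current projected sample size of 60 will be underpowered", with power 0.56.

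The randomisation list in Section 4C is "for total of 100 potential subjects". It is not linked to the 60 or to dropout. Nothing in the document says whether 60 is enrolled, randomised or evaluable.

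**The concern.** The dropout statement describes a step already taken, so a reader expects the primary sample size to contain it. On the plan's own inputs, 60 is what the formula gives before any allowance. The Aim 1 test needs both ambulatory recordings from each patient, so someone who leaves before the second contributes nothing to it. If 60 is also the number enrolled, the stated 80% power for the primary outcome is not reached once the plan's expected losses occur. If 60 is the evaluable number, the power statement holds by normal approximation but the recruitment target is nowhere stated. Either way the reader cannot check that the dropout allowance and 80% power hold together.

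**Working it through.** **Inputs.** Alpha 0.05 two-sided, power 0.80, difference 4 mmHg and SD 11 mmHg (Section 6); dropout 10-15% (Section 10, item 1(d)). The SD is a cohort SD of 24-hour systolic pressure. It is used below as the SD of paired differences, because no other value is given.

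**1. Reproduce the 60.** Paired normal formula: n = [SD × (1.960 + 0.8416) / difference]² = (11 × 2.8016 / 4)² = 59.36, rounded up to 60. This matches exactly with no inflation. By the paired t-test (noncentral t), 61 pairs give 79.8% and 62 give 80.45%, so 62 are needed.

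**2. Reproduce the 0.56.** Power at 3 mmHg with 60 pairs: Φ(3/11 × √60 − 1.960) = Φ(0.153) = 0.561. By paired t it is 0.547.

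**3. Does the 0.56 show that 60 is uninflated?** No. By normal approximation, any paired design with exactly 80% power at 4 mmHg has Φ(0.75 × 2.8016 − 1.960) = Φ(0.141) = 0.556 at 3 mmHg, whatever its n or SD. That also rounds to 0.56.

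**4. What an already inflated 60 would require.** It would mean 54 evaluable pairs (60 × 0.90) or 51 (60 × 0.85). For 80% power the SD of differences would have to be 4 × √54 / 2.8016 = 10.49 or 4 × √51 / 2.8016 = 10.20. With SD 11 in each period, SD of differences = 11 × √[2(1 − ρ)], so ρ = 0.545 or 0.570. SD 11 corresponds to ρ = 0.5. The document states no correlation.

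**5. If 60 is enrolled** (SD of differences 11):

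| Pairs | 4 mmHg, normal | 4 mmHg, paired t | 3 mmHg, normal | 3 mmHg, paired t |
|---|---|---|---|---|
| 60 | 80.4% | 79.1% | 56.1% | 54.7% |
| 54 (10% lost) | 76.2% | 74.7% | 51.8% | 50.3% |
| 51 (15% lost) | 73.8% | 72.1% | 49.5% | 48.0% |

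On the t scale dropout alone costs 79.12 − 74.65 = 4.5 points to 79.12 − 72.13 = 7.0 points. Moving from normal to t costs 80.42 − 79.12 = 1.3 points.

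**6. If 60 is evaluable.** To be randomised: 60/0.90 = 66.7, so 67; 60/0.85 = 70.6, so 71. From the paired-t base: 62/0.90 = 68.9, so 69; 62/0.85 = 72.9, so 73. All fit within the 100-place list.

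**7. Sensitivity (assumption only; SD 11 in each period).** Correlations of 0.4 to 0.6 give SDs of differences from 12.05 to 9.84, and paired-t power of 71.5-87.2% at 60 pairs and 64.2-81.3% at 51 pairs.

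**The case against.** The strongest reply is that nothing is miscalculated. Both 60 and 0.56 reproduce. Section 6 words 60 as a requirement, which suits evaluable pairs, and the list of 100 has ample room for 67-73 patients. On that reading the dropout sentence is true and only a target is missing. This reading cannot be excluded. However, the list is described only as capacity, and item 2(b) calls 60 the projected sample size, which leaves the enrolled reading open too.

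A second reply is that 60 may already include dropout. That also cannot be ruled out, but it needs the unstated correlation in step 4, while the one SD supplied gives 60 without any allowance. A reader might take the 0.56 as independent proof that all 60 are analysed; step 3 shows that it does not separate the two readings.

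A third reply is that losses may be small. Section 9 reports 17 recruited and 16 completed, without saying whether the 17th dropped out or was still in the study. At that rate 60 × 16/17 = 56.5 leaves 56 complete pairs, with 76.2% power by paired t (77.7% normal): a smaller loss, but still below 80%. Section 4C adds: "If any of the ABP or WatchPAT data is invalid or incomplete, the patient may be asked to repeat these tests". That can recover a failed recording but not a patient who has left.

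**Conclusion.** The point holds in a limited form and should be fixed. The plan claims a dropout allowance that is not visible in the number it relies on for the primary outcome. If SD 11 is the SD of paired differences and 60 is the number enrolled, power at 4 mmHg is about 72-75% by the planned test, not 80%. If 60 is evaluable pairs, no power is lost to dropout but the number to be randomised is missing.

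A reader might infer that the trial is underpowered or that the plan flatly contradicts itself. The document supports neither. The enrolled or evaluable status is unstated, the list allows more than 60, and the true SD of differences is unknown; over the assumed range in step 7 it moves power as much as dropout does, in either direction. Even the adverse reading is a modest loss and not a failed design.

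**What to change.** Change the text of Section 6 and of Section 10, items 1(d) and 2(b), so that they agree.

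- **In either case:** state in Section 6 that 11 mmHg is used as the SD of paired differences (correlation 0.5 if both periods have SD 11). If a smaller SD was in fact used and 60 already contains the allowance, give that SD and the evaluable number instead.
- **If 60 is enrolled:** restate the primary power as about 72-75% and the 3 mmHg power as about 48-50% (paired t, 51-54 pairs), and delete the claim that dropout is accounted for.
- **If 60 is evaluable pairs:** keep the claim, label the 0.56 as applying to 60 evaluable pairs by normal approximation, and state the number to be randomised as 67-71. If the paired-t requirement of 62 pairs is adopted, the number is 69-73, and the 3 mmHg power at 62 pairs is 0.56 by paired t.

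No analysis or estimand changes. The cost is a slightly less favourable power statement in the first case. In the second, if 60 had been the recruitment target, it is 7-13 more patients, within the existing list.

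Optional, and without weight here: the PEP figure of 47 matches a two-sample per-group formula (46.98), which equals a paired design with correlation 0. The systolic basis would give 24 by normal approximation or 26 by paired t. State which basis is meant.
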